#### A.1.4 Risks-Benefits from a Literature perspective

The primary objective of lumbar surgery in patients with spondylolisthesis and stenosis is to decompress the neural elements, as the patients will present symptoms such as neurogenic claudication, radiculopathy and/or low back pain(20). The available evidence contains generally a heterogeneous cohort of subjects, often combining patients with and without spondylolisthesis, treated by a variety of surgical techniques, limiting fusions to patients with instability(21). Lumbar fusion was considered appropriate to stabilize the spine in patients diagnosed with spondylolisthesis with stenosis, to avoid further misalignment, recurrence of pain and/or neurological complaints(22). For the stenosis patients that do not improve with conservative care, the role of fusion in the absence of degenerative processes was uncertain(21).

It was documented that the most common patient complications after decompression for lumbar spinal stenosis were per-operative dural lesions (23). The overall incidence for dural lesions was 7.4%, and high age, previous surgery and smoking were risk factors for sustaining a lesion. However, at 1 year FU the outcome was not affected negatively by these factors (23). Surgery for lumbar spinal stenosis in obese patients led to a clinically important (>10%) weight loss in 8% of the patients. The weight loss was not related to changes in patient-related outcomes (23). In the early 2000, the first reports were published on MIS TLIF with percutaneous pedicle screw fixation via tubular retractors, developed to avoid surgery-related lesions to the paraspinal muscle (20, 24, 25). It is well-documented and generally accepted that MIS techniques result in less blood loss, less post-operative pain, shorter hospital stay, faster recovery and fewer post-operative infections when compared with open techniques(13, 15, 26-32). A recent systematic literature review of 460 publications(33) was performed to examine the potential

complication of MIS and traditional surgery. A similar incidence of dural tears, infection, screw malpositioning, root injury and revision surgery rates was reported in both MIS and open surgery patients.

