A systematic review of 258 publications regarding lateral fusion techniques (LLIF, XLIF(R), or DLIF)(34) examining the comparative safety and effectiveness for lateral techniques concluded that there was not sufficient evidence to compare the effectiveness of LLIF versus PLIF/TLIF surgery(34). However, the patients in the LLIF group experienced less estimated blood loss and a lower mortality risk compared with the PLIF group. No permanent neurological impairment, vascular or visceral injuries were observed in 97 consecutive patients from three different centers at a mean FU of 12 months(35). A rare complication of bowel perforation for XLIF in a 70-year old male was reported(36). ALIF open lumbar interbody fusion technique was associated with retrograde ejaculation (RE), demonstrating an increased risk (6.3%) in patients which received BMP-2 than in patients that were not exposed to BMP-2 (0.9%)(37). In fact, when using the rhBMP-2 in spinal fusion surgery a 10-50 times higher risk for AE than compared with sponsored peer-review publications(38) was communicated.

Concerns have been expressed about the instrumented fusion leading to a more stiff spine, and thus, to an increased risk for adjacent segment disease (ASD). ASD requires often re-operation, and is reported to be a common problem after lumbar spine fusion. However, there was no statistically significant difference of ASD incidence in patients undergoing open or percutaneous ALIF(8). Preoperative degenerative changes and post-operative sagittal imbalance were however important factors for developing ASD(39), along with high BMI(40) with a majority of the ASD re-operations being performed > 5 years post-surgery(41). A meta-analysis demonstrated that, when comparing with motion-preserving procedures, fusion patients were at higher risk of developing ASD(42). Within 10 years after surgery, it was predicted that 10% of patients would undergo additional surgery for ASD after index lumbar fusion, with PLIF (43, 44) and age > 60 years being risk factors.

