**Device deficiency: (ISO 14155:2011 3.15)**

Inadequacy of a medical device with respect to its identity, quality, durability, reliability, safety or performance

*NOTE:* Device deficiencies include malfunctions, use errors, and inadequate labelling.

Unavoidable AE	An Adverse Event inherent to a surgical procedure that is expected to occur in all subjects for a projected duration.	
	Event Description	Timeframe (hours) from the Surgical Procedure
	Anesthesia related nausea / vomiting	24
	Low-grade fever (<100°F or 37.8°C)	48
	Sleep problems (insomnia)	72

In all geographies unavoidable AEs need not be reported unless the AE worsens or is present outside the stated timeframe post-implant. An event is not considered an AE if it has been identified as a pre-existing condition, unless the AE worsens or is present outside the stated post-Surgical Procedure timeframe.

In addition, further classification of the relationship will be done by the investigator according to the following parameters:

• **Device related:**

Events specifically related to the Devices (please see definition of AEs and Device Deficiency in Section E.9.1) including but not necessarily limited to insertion device breakage, insertion device dysfunction, cage movement-

migration, subsidence, screw breakage, screw pullout, screw dislodgement, rod breakage and inflammatory/allergic reaction to the Devices.

• **MAST™ Approach/Procedure related:**

Events specifically related to the minimally invasive surgical approach procedure including the minimally invasive access approach, decompression, and insertion of instrumentation. These events include but are not limited to local, temporary back pain caused by ligament distraction, dural tears, nerve root injury and bone fracture.

• **General Surgery related or Lumbar Fusion procedure related:**

Events related to general surgery in general who are not related to the MAST related events. These events could include but are not limited to, hematoma, wound pain, wound breakdown and infection.

• **Related to the disease:**

AEs related to the progression of degenerative lumbar spine. These events include but are not limited to recurrence of symptoms due to further degeneration of a previously healthy level leading to symptoms occurrence.

AE not related to diseases should be collected as well.

The above relationship parameters will be assessed and categorized as per the MEDDEV 2.7/3 levels of causality:

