#### **G.1.2 Analysis of Secondary Endpoints**

For the first secondary objective, the similar method as the one outlined above for the primary endpoint will be used to assess whether the ODI improvement at 3 months is equivalent for the non-spondylolisthesis DDD subjects treated with anterolateral approaches and the ones treated with posterior approaches.

For secondary points ODI improvement at other follow-ups other than at 3-months visit; change of VAS back and leg pain intensity and EQ-5D at all follow-ups through 5-year visit, summary statistics will be provided and the paired t-test will be used to test whether the improvement at each follow-up from baseline is significant.

The neurological success rate will be summarized at each follow-up. Overall neurological success will be defined as maintenance or improvement in all sections (motor, sensory, reflex, and straight leg raising) for the time period evaluated. In order for a section to be considered a success, each element in the section must remain the same or improve from the time of the baseline evaluation to the time period evaluated. Therefore, if any one element in any section does not stay the same or improve, then a patient will not be considered a success for neurological status.

Time-to-event-analysis will be conducted for fusion success. The fusion success rate will be summarized for 1, 2, 3, 4, 5-year follow-up, if applicable. If a subject shows fusion success at early timepoints and non-fusion at a later timepoint, the fusion status at all earlier time points should be considered as non-fusion.

For 2-level subjects, fusion success will be defined as achieving fusion at both treated levels.

For secondary surgery at index levels, secondary surgery at adjacent levels and AEs, survival analysis will be performed to estimate the cumulative event rate up to 5 years.

Healthcare utilization will be measured with the following three cost components:

- (1) resources: procedure, length of hospital stay, additional medical visits (outpatient consultations, visits to primary care services, etc)
- (2) medications and
- (3) non-pharmacologic therapies: rehabilitation program

For time needed for first ambulation and surgery recovery day, summary statistics for continuous variable will be provided by subgroups.

The analyses for the primary endpoint and secondary endpoints outlined in secondary objectives 2 and 3 will be done for all subjects and the following subgroups:

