6.1.3. Analysis Datasets

The primary analysis dataset defined in this study comprises of all subjects who are enrolled and receive a single or double level instrumented fusion using MAST™ minimally invasive PLIF, TLIF, DLIF, OLIF, ALIF and MIDLIF surgical procedures with a mandatory posterior fixation. For double levels instrumented fusion, the same procedure must be used for both levels. All the analyses will be carried out on the

This document is electronically controlled. Printed copies are considered uncontrolled.

Confidential

primary analysis dataset. For subjects who are enrolled but not included in the primary analysis dataset, their demographic and other baseline characteristics will be summarized separately. The reasons for not using minimally invasive procedure or surgery not done will be listed as well.

In addition to the primary analysis dataset, four subgroups are defined in the following:

- 1) DDD patients with spondylolisthesis and stenosis
- 2) DDD patients with spondylolisthesis but without stenosis
- 3) DDD patients with stenosis but without spondylolisthesis
- 4) All patients not included in subgroups 1), 2), 3).

The analysis for the primary endpoint and secondary endpoints outlined in secondary objectives 2 and 3 (section 4.2) will be performed on these four subgroups as well. For the primary analysis dataset and each of these four subgroups, the analysis will be carried out on further subgrouped by anterolateral and posterior groups.

Other subgroup analysis such as by number of treated levels may also be performed.

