6.9.2.2.5. Adverse events

Detailed information about how AEs will be summarized can be found in section 6.10.

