6.10. Safety Evaluation

The analyses include:

- Time-to-event (life table method) to assess the cumulative AE rate up to 4-week, 1-year, 2-year, 3-year, 4-year and 5-year visit intervals.
- Summary of number of AEs and number of subjects having AEs up to the 5-year visit.
 - All AEs
 - Serious Adverse Events (SAE)
 - Device related AEs
 - MAST™ Approach/Procedure related AEs
 - General Surgery related or Lumbar Fusion procedure related AEs
 - Disease related AEs.
 - Serious device related AEs
 - Serious MAST™ Approach/Procedure related AEs

A relatedness determination of "possible", "probable" or "causal relationship" is considered "related".

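### SAP 6.10 counts adverse events by seriousness and attribution but not by type, so most harms the CIP names get no rate of their own and a difference between approaches can be hidden within a class or a total

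*SAP*

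**What the plan says.** Adverse events are an endpoint of secondary objective 2 (CIP B.1.3, SAP 4.2). SAP 6.9.2.2.5 contains no analysis of its own: "Detailed information about how AEs will be summarized can be found in section 6.10".

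SAP 6.10 gives two outputs:

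- "Time-to-event (life table method) to assess the cumulative AE rate up to 4-week, 1-year, 2-year, 3-year, 4-year and 5-year visit intervals". This is not split by event type.
- "Summary of number of AEs and number of subjects having AEs up to the 5-year visit", on eight lines: all AEs; SAEs; device related; MAST approach/procedure related; general surgery or lumbar fusion procedure related; disease related; serious device related; serious MAST related.

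CIP G.1.2 is no more specific: "For secondary surgery at index levels, secondary surgery at adjacent levels and AEs, survival analysis will be performed". Neither SAP 6.10 nor CIP G.1 names an event term, a coding dictionary or a list of events of interest.

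The split by approach is already planned. For the endpoints of objectives 2 and 3, SAP 6.1.3 says that "the analysis will be carried out on further subgrouped by anterolateral and posterior groups".

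**The concern.** Describing long-term safety is one of the two study aims (CIP B.1.1, SAP 4), and the CIP names the harms it has in mind. A.1.4 discusses dural lesions, retrograde ejaculation after ALIF, infection, and vascular or visceral injury, including a bowel perforation with a lateral approach. E.9.1.1 lists cage migration, subsidence, screw and rod breakage, nerve root injury and others as examples of its attribution classes.

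Those classes answer the question of what an event is attributed to. They do not say what happened to the patient. Examples given for the MAST class are "local, temporary back pain caused by ligament distraction, dural tears, nerve root injury and bone fracture", so a passing complaint and a nerve root injury count alike on that line. A reader of the report could see how many patients in each approach had a MAST-related event, but not how many had a dural tear. If the approaches differ in which harms they cause rather than in how many, the planned summary may not show it.

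**Working it through.** **Step 1. Where each named harm would be counted.**

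| Harm | Named in CIP | Line in SAP 6.10 | Own rate anywhere in the plan? |
|---|---|---|---|
| Dural tear | A.1.4, E.9.1.1 | MAST class, with temporary back pain, nerve root injury and bone fracture | No |
| Nerve root injury | E.9.1.1 | Same class | Not as an AE; deterioration on examination is shown by section at each visit (SAP 6.9.2.2.2) |
| Infection | A.1.4, E.9.1.1 | General surgery class, with haematoma and wound events | No |
| Cage migration or subsidence, screw or rod failure | E.9.1.1 | Device class, pooled | No, except where it leads to secondary surgery |
| Vascular or visceral injury | A.1.4 | No class stated | No |
| Retrograde ejaculation | A.1.4 | No class stated | No |
| Secondary surgery | B.1.3 | Not applicable | Yes, life table (SAP 6.9.2.2.4) |

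**Step 2. Can a class line hide a difference? A purely hypothetical example.**

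Inputs: 350 patients planned (CIP B.7). An equal split of 350/2 = 175 per approach is assumed. The 7.4% is borrowed from the dural-lesion figure in CIP A.1.4 only to have a plausible size; it comes from decompression for stenosis and is not an expected rate here. The contrasting rate of 1% (then 2%), the mirrored pattern and independence of the two harms are all assumptions.

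Harms A and B fall in the same class. A occurs in 7.4% of posterior and 1% of anterolateral patients; B is the reverse.

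- Patients with either harm, in each approach: 1 − (1 − 0.074)(1 − 0.01) = 1 − 0.9167 = 8.3%.
- Counts per harm: 175 × 0.074 = 12.95, about 13; 175 × 0.01 = 1.75, about 2.
- Class line: 13 + 2 = 15 events against 2 + 13 = 15, so no difference.
- By type: 13/175 against 2/175 for each harm, Fisher exact p = 0.006.
- With 2% in place of 1%: the class line is 17 against 17 events; by type it is 13 against 4, p = 0.04.

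**Step 3. Dilution without cancelling.**

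Suppose only one harm differs, 7.4% against 1%, and a share b of patients has some other AE. The any-AE rate is 1 − (1 − b)(1 − harm rate).

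| Assumed b | Any-AE rates | Power to see the difference, 175 per approach |
|---|---|---|
| 30% | 35.2% vs 30.7% | about 14% |
| 60% | 63.0% vs 60.4% | about 7% |
| 80% | 81.5% vs 80.2% | about 5% |

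The same single harm tabulated by type has power of about 85%.

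**Step 4. What a by-type line could deliver.**

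An observed 13/175 is 7.4% with a 95% Clopper-Pearson interval of 4.0% to 12.4%; 26/350 gives 4.9% to 10.7%. No event in 175 patients gives an upper limit of 2.1%. These are usable descriptive estimates for harms of that order.

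**The case against.** Much of the case on the other side stands and limits the point.

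- **Some typed outputs exist.** Neurological status is reported by section with deterioration as a category, and secondary surgery has its own life table. It would be wrong to infer that no specific harm is visible. Neither output, however, gives a rate for dural tear, infection, visceral injury or retrograde ejaculation, and an examination at a visit can miss a nerve injury that has resolved.
- **The classes separate some harms.** Device failures, infection and dural tears fall under different headings in CIP E.9.1.1. A reader might infer that any harm in one approach can cancel any harm in the other. On the class lines that does not follow: an excess of hardware failure cannot offset dural tears there. Cancelling is confined to harms within a class and to the all-AE and SAE totals.
- **The plan makes no claim of equal safety.** A reader might infer that balanced totals would be reported as equivalence. CIP B.4 states no hypothesis for the other secondary objectives; equivalence is tested only on ODI at 3 months.
- **The literature rates are not forecasts.** The 7.4% is from decompression for stenosis. The retrograde ejaculation figures in A.1.4 (6.3% with BMP-2, 0.9% without) are for open ALIF, and the bowel perforation is a single case. They show that the harms are known, not how often they will occur in this study.
- **Nothing forbids a by-type table.** The list in SAP 6.10 is worded as inclusive, and SAP 6.2 allows frequency tables for categorical variables. That is so, but SAP 6.9.2.2.5 names 6.10 as the detailed specification. A table left out of it would be optional and could be designed after the data are seen.

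**Conclusion.** The point holds in a limited form. AE summaries are already planned by approach; what is missing is the event-type dimension. Apart from neurological status and secondary surgery, the specific harms named in the CIP get no rate under the plan as written, and differences between approaches can be hidden within a class or in the all-AE and SAE totals.

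That the classes pool unlike events follows directly from the text. How much would be hidden in this study cannot be known from the documents: the 8.3% against 8.3% example rests on invented mirrored rates and an assumed equal split, and shows only that masking is possible. The documents do not support the stronger conclusions that the approaches are not compared on safety at all, or that the plan would declare them equally safe. No hypothesis, endpoint definition or sample size is affected. This is a worthwhile, cheap improvement to how a stated aim is answered.

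**What to change.** Add to SAP 6.10 a descriptive table by approach (anterolateral, posterior) giving the number of events and the number and percentage of patients by AE type, once for all AEs and once for SAEs. Type may be the eCRF category or a coded or grouped term; the SAP should say which, and fix the grouping before the tables are run.

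Give separate lines to the harms the CIP names: dural tear; nerve root injury; infection; vascular or visceral injury; retrograde ejaculation, with male patients as denominator; cage migration or subsidence; screw or rod failure. The existing lines by seriousness and attribution stay.

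Cost: SAP wording and one or two tables. CIP E.9.1.2 has one AE form per event, so no new visit is needed. The content of the AE form is not in the documents, so whether a category or code is captured must be checked; if not, terms have to be grouped from the reported descriptions, consistently across sites.

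Some cells will be sparse. For example, assuming 350/6, about 58 ALIF patients, of whom half (29) are men, the A.1.4 rates of 0.9% and 6.3% would correspond to 0.3 to 1.8 cases of retrograde ejaculation. The line is worth having for transparency, but a further split by bone-graft type would tell the reader nothing and is not proposed.

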6.11. Health Outcomes Analyses

Please refer to session 6.9.2.4..

6.12. Changes to Planned Analysis

This section is not applicable.

This document is electronically controlled. Printed copies are considered uncontrolled.

Confidential

7. Validation Requirements

For interim and final report, level I validation will be applied for all statistical analyses in this study, which means that the peer reviewer will independently write statistical programs, generate results and then compare the output with the one generated by the primary statistician.

Progress reports, such as annual report, are intended to include as much and the latest data as possible, including data that have not been monitored, cleaned or finalized. Thus, these reports will not be validated by using independent programming. Instead level III validation will be used, which means that the primary statistician will perform a visual inspection of the code and output to confirm functionality.

For any manuscript publication, level I validation will be applied with independent programming from peer reviewer.

Please refer to work instruction 056-WI181, "Statistical Programming Code Quality Control and Validation" for details.

This document is electronically controlled. Printed copies are considered uncontrolled.

Confidential
